#### Risk of Serious Adverse Reactions in Pediatric Patients due to Benzyl Alcohol Preservative:

Gasping syndrome (central nervous system depression, metabolic acidosis and irregular respiration) is a serious and potentially fatal adverse reaction in infants treated with benzyl alcohol-preserved drugs. The 7 days bag of BLINCYTO solution for infusion with benzyl alcohol is not recommended for use in pediatric patients weighing < 22 kg. Consider the combined daily load of benzyl alcohol from all sources (including BLINCYTO) when prescribing BLINCYTO to pediatric patients.

#### 3.1.2 Blinatumomab dosage, administration, and schedule

Blinatumomab is administered as a continuous intravenous infusion (CIV). A single cycle of blinatumomab treatment is 4 weeks of CIV. Since patients are either in remission, or have minimal residual disease at time of treatment, the dosing schedule for minimal residual disease will be followed. Additionally, since both children and adults will be treated on this study, dosing will be weight- and BSA-based as per FDA guidelines for this drug. Please see section 5.3 for details of dosing administration.

The drug administration should not be interrupted, if possible. In case of infusion interruption, due to any technical or logistic reason, the interruption should be as short as possible and the infusion continued at the earliest time possible. Every interruption longer than 1 hour should be documented. If the interruption is longer than 4 hours, re-start of the infusion should be performed under healthcare supervision. The patient should be observed overnight for possible side effects after the restart in the hospital. Administration of dexamethasone premedication as described in Table 3 is recommended. If possible, the infusion duration before and after an interruption should total 28 days per treatment cycle.

### 3.1.3 Blinatumomab inpatient dosing

It is recommended that subjects are hospitalized at least during the first 3 days of the first induction cycle and the first 2 days of the following cycles.

The infusion bags will be changed by site nursing personnel trained on the protocol and on the proper administration of blinatumomab. Close monitoring during the first 48 hours of treatment in the first 2 cycles will be indicated because of the potential adverse events associated with T-cell redistribution and potential cytokine release effects triggered by the administration of blinatumomab.

### 3.1.4 Blinatumomab outpatient dosing

After a patient meets the minimum criteria for inpatient administration and monitoring as described in the above section, and if a subject is deemed stable by the Principal Investigator or designee, continuation of blinatumomab infusion may continue as an outpatient.

In the outpatient setting, either the subject will return to the study site for changes of infusion bags or the subject will be visited by a well-trained ambulant/home care service provider at specific intervals to change the infusion bag. The subject and the ambulant/home care provider will be trained and will receive written instructions for storage of the IV bags.

In the event of drug interruptions of >4 hours, the restart of the infusion should be performed in the clinic/hospital under the supervision of their healthcare provider.

In case of any adverse event in the outpatient setting, the ambulant/home care provider should directly contact their healthcare provider at the study center for further management.

## 3.2 Dexamethasone premedication

Premedication with dexamethasone is intended to prevent CRS events associated with blinatumomab treatment. Within 1 hour before the start of treatment in each treatment cycle, mandatory premedication with dexamethasone at 20 mg IV if  $\geq 45$  Kg (or 5 mg/m^2 to a maximum of 20 mg if  $< 45$  Kg) IV is required for the prevention of CRS resulting from blinatumomab (Table 1).

### 3.3. Dose modifications (interruptions, withholdings, and criteria for restarting treatment) (Tables 1 and 2).

#### 3.3.1 Infusion interruption/dose modification due to adverse events

Common Terminology Criteria for Adverse Events (CTCAE) grade 4 adverse events at least possibly related to blinatumomab will require permanent

discontinuation of blinatumomab. For CTCAE grade 4 adverse events that are numerically defined laboratory parameters, independent investigator assessment should be used to determine the risk: benefit for each individual patient to continue or discontinue blinatumomab treatment.

For CTCAE grade 3, cytokine release syndrome, and CTCAE grade 3 DIC/coagulopathy, treatment with blinatumomab will be interrupted until the event resolves to at least grade 1. Blinatumomab can then be restarted at the lowest starting dose (9 µg/day if  $\geq$  45 Kg or 5 µg/m^2/day if  $<$  45 Kg). If the AE lasts for  $\geq$  2 weeks, then blinatumomab will be permanently discontinued.

For all other CTCAE grade 3 events and clinically significant laboratory value changes, investigator assessment should be used to determine the risk: benefit to continue blinatumomab therapy with or without dose reduction or discontinue therapy.

Patients who have been dose reduced will have an option to receive the higher dose level once the AE has resolved to grade 1 or less for at least 7 days. Re-start of the infusion should be performed in the hospital. Before blinatumomab is restarted, premedication with dexamethasone 20 mg if  $\geq$  45 Kg (or 5 mg/m^2 if  $<$  45 Kg) IV is required. The patient should be observed overnight for possible side effects after the restart in the hospital.

In addition to the events described above, the dose may be temporarily or permanently reduced to 9 µg/day if  $\geq$  45 Kg (or 5 µg/m^2/day if  $<$  45 Kg) if, by investigator's judgment, it is necessary for safety reasons. After at least 7 days of dosing at 9 µg/day if  $\geq$  45 Kg (or 5 µg/m^2/day if  $<$  45 Kg), the dose may be increased to 28 µg/day if  $\geq$  45 Kg (or 15 µg/m^2/day if  $<$  45 Kg) or treatment may be continued at the dose of 9 µg/day after consultation with the investigator.

If the interruption after an adverse event is no longer than 7 days, the same cycle will be continued. The infusion duration, before and after an interruption, should total 28 days per treatment cycle. If an interruption due to an adverse event is longer than 7 days, a new cycle will start. In addition, an incomplete treatment cycle with a treatment duration of less than 2 weeks will have to be repeated (eg, if cycle 1 was interrupted on day 8 for more than 7 days, the next cycle will be denoted as cycle 1.1 and the same assessments will be performed as in cycle 1). For cycle 1.1, subjects will be started at 9 µg/day if  $\geq$  45 Kg (or 5 µg/m^2/day if  $<$  45 Kg) for the first 7 days of dosing followed by a dose step to 28 µg/day if  $\geq$  45 Kg (or 15 µg/m^2/day if  $<$  45 Kg) beginning at day 8 and continuing for the remainder of cycle 1.

An infusion interruption of more than 2 weeks due to an adverse event related to blinatumomab will lead to permanent discontinuation of treatment. In case of logistical difficulties, restart of treatment can be postponed for up to 5 additional days without resulting in permanent treatment discontinuation.

Treatment may be also interrupted or permanently discontinued at the discretion of the investigator if any clinical/laboratory adverse event is considered to be medically relevant.

In case of signs of cytokine release, dexamethasone should be administered orally or IV at a dose of at maximum 3 x 8 mg/day for subjects  $\geq$  45 Kg (or 0.2-0.4 mg/kg/day divided 3-4 times per day not to exceed 24 mg/day for subjects  $<$  45 Kg) for up to 3 days. The dose can then be reduced step-wise over 4 days.

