## 2.5 Blinatumomab toxicity profile

The toxicity profile of blinatumomab has been largely consistent with historical studies, with fever, chills, and hypogammaglobulinemia occurring frequently. Tremor, headache, and other mental status changes (e.g., confusion) have been reported. Fever, chills, and other constitutional symptoms are thought to be due to a cytokine release syndrome that occurs shortly after the start of therapy and are reduced with the use of steroids (e.g. dexamethasone 8-24 mg daily x 2-3 days). The adverse effects coincided with a rapid rise in activated T-cells after blinatumomab initiation, essentially confirming the hypothesis (22). Life-threatening neurologic adverse events were uncommon and generally reversible, but seizures have been observed in both the MRD and the active disease studies. Corticosteroids before the first dose and prior to dose escalation ameliorate some of the toxicities.

The adverse reactions in pediatric patients treated with blinatumomab were similar to those seen in adult patients with relapsed or refractory B-cell precursor ALL. Adverse reactions that were observed more frequently in the pediatric population compared to the adult population were pyrexia (80% vs. 61%), hypertension (26% vs. 8%), anemia (41% vs. 24%), infusion-related reaction (49% vs. 34%), thrombocytopenia (34% vs. 21%), leukopenia (24% vs. 11%), and weight gain (17% vs. 6%). In infants and children < 2 years of age, the incidence of neurologic toxicities was not significantly different than for the other age groups, but its manifestations were different (agitation, headache, insomnia, somnolence, and irritability). In the phase I/II open label blinatumomab study in pediatric patients with relapsed / refractory ALL, among the 70 pediatric patients treated on the trial, the most frequent grade 3 adverse events were anemia (36%), thrombocytopenia (21%), and hypokalemia (17%). Three patients (4%) and one patient (1%) had cytokine-release syndrome of grade 3 and 4, respectively. Two patients (3%) interrupted treatment after grade 2 seizures. Reports of compassionate use of blinatumomab in pediatric patients with relapsed / refractory ALL and prior ASCT have shown that blinatumomab did not induce nor exacerbate acute graft versus host disease (24, 25).

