**Table 2. Management of Toxicity and Blinatumomab Dosage Adjustments**

Toxicity	Grade	Action	
		Patient Weight	
		≥ 45 Kg	< 45 Kg
Cytokine Release Syndrome (CRS)	Grade 3	Withhold blinatumomab until resolved, then restart blinatumomab at 9 mcg/day. Escalate to 28 mcg/day after 7 days if the toxicity does not recur.	Withhold blinatumomab until resolved, then restart blinatumomab at 5 $\mu\text{g}/\text{m}^2/\text{day}$ . Escalate to 15 $\mu\text{g}/\text{m}^2/\text{day}$ after 7 days if the toxicity does not recur.
	Grade 4	Discontinue blinatumomab permanently	
Neurological Toxicity	Seizure	Discontinue blinatumomab permanently if more than one seizure occurs	
	Grade 3	Withhold blinatumomab until no more than Grade 1 (mild) and for at least 3 days, then restart blinatumomab at 9 mcg/day. Escalate to 28 mcg/day after 7 days if the toxicity does not recur. If the toxicity occurred at 9 mcg/day, or if the toxicity takes more than 7 days to resolve, discontinue blinatumomab permanently.	Withhold blinatumomab until no more than Grade 1 (mild) and for at least 3 days, then restart blinatumomab at 5 $\mu\text{g}/\text{m}^2/\text{day}$ . Escalate to 15 $\mu\text{g}/\text{m}^2/\text{day}$ after 7 days if the toxicity does not recur. If the toxicity occurred at 5 $\mu\text{g}/\text{m}^2/\text{day}$ , or if the toxicity takes more than 7 days to resolve, discontinue blinatumomab permanently.
	Grade 4	Discontinue blinatumomab permanently	
Other Clinically Relevant Adverse Reactions	Grade 3	Withhold blinatumomab until no more than Grade 1 (mild), then restart blinatumomab at 9 mcg/day. Escalate to 28 mcg/day after 7 days if the toxicity does not recur. If the toxicity takes more than 14 days to resolve, discontinue blinatumomab permanently.	Withhold blinatumomab until no more than Grade 1 (mild), then restart blinatumomab at 5 $\mu\text{g}/\text{m}^2/\text{day}$ . Escalate to 15 $\mu\text{g}/\text{m}^2/\text{day}$ after 7 days if the toxicity does not recur. If the toxicity takes more than 14 days to resolve, discontinue blinatumomab permanently
	Grade 4	Discontinue blinatumomab permanently	

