## 5.0 Treatment Plan

5.1 This is an open-label, single-arm, phase II clinical study.

5.2 All patients will be registered through Core. All of the enrolled subjects' concomitant medications will be collected and readily available in the MDACC electronic medical record and will not be entered into the CRF.

5.3 Patients will receive blinatumomab as continuous intravenous infusion over 4 weeks.

Since this study includes children and adults, dosing will be weight and BSA-based as per FDA approved dosing guidelines:

**For patients  $\geq 45$  kg**, the dose is 28 mcg/day administered as a continuous infusion on days 1-28 of each cycle.

**For patients  $< 45$  kg** the dose is 15 mcg/m^2/day (maximum 28 mcg/day) administered as a continuous infusion on days 1-28 of each cycle

All patients will receive 4 cycles of blinatumomab, with first cycle administered within the first 3 months following HCT, and then at 6 (+/- 2 weeks), 9 (+/- 2 weeks), and 12 (+/- 2 weeks) months following HCT (day of hematopoietic progenitor cell infusion). This schedule was selected to allow for treatment with blinatumomab during the one year following transplant when patients are at risk for relapse while the GVL effect is maturing and becoming robust.

5.4 GVHD prophylaxis will be as institutional standard.

5.5 CNS prophylaxis will be as institutional standard. However, craniospinal radiotherapy for prophylaxis post HCT is not permitted.

5.6 Tyrosine kinase inhibitor (TKI) use for patients with Ph+ ALL will be left to the investigator's discretion.

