### 9.3 Adverse events (toxicities) known to be produced by other treatment components:

The following events are not considered to be significant in relationship with the study treatment, would not be considered adverse events, and will not be collected in the study database.

Myelosuppression-related: neutropenia, anemia thrombocytopenia, platelets and RBCs transfusions.

Flu-like symptoms: low grade fever, headache, chills, cough, rhinitis, myalgia, fatigue, sweating and insomnia.

Mood alteration: depression, anxiety, and agitation

Readmissions (lasting <10 days)

Low blood pressure due to dehydration requiring fluid replacement

Fluid overload.

Fatigue.

Laboratory serum metabolic values not reflecting end-organ (hepatic, renal)

function and or those considered associated to the original disease

Events that are identified to be related to the supportive treatment, e.g., steroids, palifermin, antibiotics.

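### For a clinically relevant grade 3 reaction (not CRS, DIC/coagulopathy or CNS), section 3.3.1 lets blinatumomab continue while Table 2 requires a hold, and neither is said to govern

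*Combined protocol and SAP*

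**What the plan says.** Section 3.3.1 makes interruption compulsory for two kinds of grade 3 event, CRS and DIC/coagulopathy. CNS events have their own rules in section 3.3.2. For every other grade 3 event, and for laboratory changes of clinical significance, section 3.3.1 states that "investigator assessment should be used to determine the risk: benefit to continue blinatumomab therapy with or without dose reduction", with discontinuation as the remaining option. Later in the same section, for events thought medically relevant: "Treatment may be also interrupted or permanently discontinued at the discretion of the investigator".

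Table 2 has a row for other clinically relevant adverse reactions. At grade 3, for patients of 45 kg or more, it reads: "Withhold blinatumomab until no more than Grade 1 (mild), then restart blinatumomab at 9 mcg/day". The dose returns to 28 mcg/day after 7 days without recurrence. The row ends: "If the toxicity takes more than 14 days to resolve, discontinue blinatumomab permanently". Under 45 kg the steps are the same, with 5 and 15 mcg/m²/day.

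The heading of section 3.3 points to Tables 1 and 2 but does not rank text and table. Clinical relevance is not defined.

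**The concern.** Two clinicians following the same protocol could treat the same reaction differently. One, relying on section 3.3.1, keeps the patient on 28 mcg/day without a break. The other, relying on Table 2, stops the infusion, waits for grade 1 and restarts at 9 mcg/day. Neither has deviated from the text being followed. At stake is whether the safeguards attached to a hold apply to a patient with a significant drug reaction. Toxicity attributable to blinatumomab is part of the primary feasibility objective (sections 1.1 and 8.2), so such reactions should be handled the same way throughout.

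**Working it through.** The plan gives no figure on this point to reproduce. The check compares the two instructions and then sizes the dose consequence.

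**1. Do the scopes overlap?** Section 3.3.1 covers all grade 3 events left after CRS and DIC/coagulopathy, with CNS events in 3.3.2. It neither exempts clinically relevant reactions nor refers them to Table 2. The Table 2 row covers grade 3 reactions that are clinically relevant. A reaction with that label falls under both.

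**2. Can both be followed?**

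| Choice open under 3.3.1 | Consistent with the Table 2 row? |
|---|---|
| Interrupt to grade 1, restart low, re-escalate | Yes |
| Continue at full dose | No: no hold, no low-dose restart |
| Reduce the dose without a hold | No: no hold |
| Discontinue permanently | Table 2 directs this only after 14 days; it errs toward less drug |

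The conflict is therefore confined to continuation without a break.

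**3. What is skipped?** Under section 3.3.1 a restart takes place in hospital, after dexamethasone, with overnight observation. Table 1 requires dexamethasone before restart after an interruption of more than 4 hours. Full-dose continuation triggers none of this. The 14-day limit in Table 2 runs on duration of the toxicity. The two-week limits in 3.3.1 (interruption due to a related event) and in removal criterion 7.4 run on length of interruption. If the infusion is never interrupted, those two cannot apply. The two-week rule on duration of the event in 3.3.1 sits in the CRS and DIC/coagulopathy paragraph.

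**4. Dose consequence, one affected cycle.** Inputs: 28 mcg/day for 28 days and four cycles (section 5.3: "All patients will receive 4 cycles of blinatumomab"); 9 mcg/day for 7 days after restart (Table 2); the cycle rule of 3.3.1: "If the interruption after an adverse event is no longer than 7 days, the same cycle will be continued", to a total of 28 infusion days.

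*Hold of 7 days or less, at least 7 infusion days left, 45 kg or more:*
- Full-dose continuation: 28 × 28 = 784 mcg.
- Table 2 path: 7 × 9 + 21 × 28 = 651 mcg.
- Difference: 784 − 651 = 133 mcg; 133/784 = 17.0% of the cycle; 133/(4 × 784) = 133/3136 = 4.2% of four cycles.
- Seven days at 9 mcg/day without a hold, then 28 mcg/day: also 651 mcg, difference zero.
- Permanent reduction after 14 full-dose days: 14 × 28 + 14 × 9 = 518 mcg, below the Table 2 path.
- Discontinuation after 14 full-dose days: 14 × 28 = 392 mcg, also below it.

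*Same hold, under 45 kg and below the 28 mcg/day cap:* 28 × 15 = 420 against 7 × 5 + 21 × 15 = 350 mcg/m². The difference is 70, or 16.7% of the cycle and 70/1680 = 4.2% of four cycles.

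*Hold of more than 7 and up to 14 days, 45 kg or more:* section 3.3.1 starts a new cycle and repeats one with under two weeks of treatment.
- Event after 7 full-dose days: 7 × 28 + 651 = 847 mcg, which is 63 mcg more than 784.
- Event after 14 full-dose days, no repeat required: 392 mcg, 50% of 784.

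*Resolution after more than 14 days:* Table 2 ends treatment and all later cycles are lost; section 3.3.1 would let them proceed.

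**5. How many patients?** The documents give no grade 3 rate for this post-transplant population. The rates in section 2.5 (anemia 36%, thrombocytopenia 21%, hypokalemia 17%) come from children with relapsed or refractory disease.

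**The case against.** The strongest reply is that to continue therapy, set against discontinuing it, can mean staying on the treatment program. Table 2 would then supply the mechanics of hold and restart. The next paragraph of 3.3.1 does describe restarts, so holds are contemplated. This reading fails on the words allowing continuation without dose reduction, because Table 2 always restarts at the low dose. The optional wording on interruption also points away from a compulsory hold.

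A second reply is that the investigator first decides which events are clinically relevant and sends those to Table 2. That is workable, and the fix below adopts it, but the protocol does not say it. It also leaves clinical relevance to judgment, and the fix does not remove that.

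A reader might infer three stronger things. None is supported.
- That the contradiction covers all grade 3 events. Grade 3 CRS, DIC/coagulopathy and CNS events have compulsory holds, and events judged not clinically relevant fall outside the Table 2 row.
- That patients would receive 17% more drug under 3.3.1. Other permitted choices, or a longer hold, give equal doses or reverse the sign.
- That section 9.3 shows the reach to be negligible, because the events it lists "would not be considered adverse events, and will not be collected in the study database". That section governs reporting. It does not exempt events from the dose rules, so it cannot size the reach in either direction.

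**Conclusion.** The inconsistency is real and should be corrected, within a limited range: a grade 3 reaction that is judged clinically relevant, is not CRS, DIC/coagulopathy or a CNS event, and is continued without a hold. Its weight lies in the safeguards that may be bypassed. The dose effect has no fixed size or direction. The 133 mcg (17% of one cycle, 4.2% of four) assumes a patient of 45 kg or more, a hold of 7 days or less, at least 7 infusion days left, one affected cycle, and full-dose continuation as the alternative. The number of patients affected cannot be estimated from the documents.

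A reader might also infer that the stopping rule or the feasibility conclusion is compromised. The toxicities monitored in section 8.3.5 are severe acute GVHD, secondary graft failure and early non-relapse mortality. The boundaries in Table 5, the operating characteristics in Table 6 and the planned analyses do not depend on which dosing instruction is followed.

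**What to change.** Replace the sentence in section 3.3.1 on the remaining grade 3 events with:

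> Grade 3 adverse reactions other than CRS, DIC/coagulopathy and CNS events that the investigator judges clinically relevant follow the Table 2 row. For the remaining grade 3 events, and for clinically significant laboratory value changes that are not such grade 3 reactions, the investigator decides whether to continue at full or reduced dose, or to discontinue. Where Table 2 and this paragraph differ, Table 2 governs.

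In the later sentence of 3.3.1 on discretion, state that interruption is optional only for events outside the compulsory holds of 3.3.1, 3.3.2 and Table 2, and that the investigator may still discontinue permanently for any medically relevant event. Keep the precedence statement to this paragraph, so that it does not alter the CNS rules in 3.3.2.

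The documents do not show which rule was intended. If the sponsor meant to leave discretion, Table 2 could be amended instead, but one instruction must govern; the wording above keeps the more protective one. The cost is protocol wording in 3.3.1, somewhat less investigator discretion and some additional holds. The Table 2 entries, sample size, stopping rule and analyses stay as they are.

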### 3.3.2 Infusion interruption/dose modification due to CNS events

In case of CNS-related adverse events, dexamethasone should be administered at a dose of at least 24 mg/day for subjects  $\geq$  45 Kg (or 0.2-0.4 mg/kg/day divided 3-4 times per day not to exceed 24 mg/day for subjects  $<$  45 Kg). The dexamethasone dose will then be reduced step-wise over 4 days.

In case of CTCAE grade 3 or higher CNS-related adverse events, blinatumomab will be stopped immediately and a physical exam, vital signs and safety laboratory tests will be performed. Additional measures can be taken upon discretion of the investigator, depending on the nature of the adverse event. Diagnostic measures to exclude potential infectious causes should be conducted after CNS events  $\geq$  CTCAE grade 3; an assessment of cerebrospinal fluid should be performed for cytology, cell count, B- and T-cell measurement (flow cytometry at local lab), and viral studies (HSV 1/2, HSV6, JC virus and adenovirus), and magnetic resonance imaging (MRI).

Patients, who had experienced a Grade 3 CNS AE or SAE leading to treatment interruption, should have a treatment free interval of two weeks, even if the event has resolved to Grade 1 earlier. These patients will have to undergo MRI before treatment is resumed. Infusion should be re-started in the hospital, under supervision of the investigator and the patient should remain hospitalized for at least two days.

Following dexamethasone premedication, a new treatment cycle will start with a dose of 9  $\mu$ g/day if  $\geq$  45 Kg (or 5  $\mu$ g/m^2/day if  $<$  45 Kg). Blinatumomab will be escalated to 28 mcg/day if  $\geq$  45 Kg (or 15  $\mu$ g/m^2/day if  $<$  45 Kg) after 7 days if the toxicity does not recur. If the toxicity occurs at 9 mcg/day if  $\geq$  45 Kg (or 5  $\mu$ g/m^2/day if  $<$  45 Kg), or if the toxicity takes more than 7 days to resolve, blinatumomab therapy will be stopped permanently.

If the CNS event was a seizure (CTCAE grade 2 or above), appropriate prophylactic anticonvulsant treatment will be administered during the next treatment cycle.

A grade 3 CNS event leading to treatment interruption at the dose of 9 µg/day if  $\geq$  45 Kg (or 5 µg/m^2/day if  $<$  45 Kg) or a CNS event needing more than 1 week to resolve to grade  $\leq$  1 will result in permanent treatment discontinuation.

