## 7.0 Criteria for Removal from the Study

7.1 Completion of study at 1 year.

7.2 Non-compliance by the patient with protocol requirements.

7.3 Occurrence of CTCAE grade 4 adverse event probably or definitely related to blinatumomab.

7.4 An infusion interruption of more than 2 weeks due to an adverse event related to blinatumomab.

7.5 Occurrence of a CNS-related adverse event probably or definitely related to blinatumomab, and meeting one or more of the following criteria:

- More than 1 seizure
- A CNS-related CTCAE Grade 4 adverse event
- A CNS-related adverse event leading to treatment interruption that requires more than one week to resolve to CTCAE Grade  $\leq 1$
- A CTCAE Grade 3 CNS-related adverse event leading to treatment interruption that occurred at a dose of 9 $\mu$ g/day

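### Two of the protocol's 13 statements of the blinatumomab low dose (one in 3.3.1, one in 7.5) print only 9 µg/day and omit 5 µg/m²/day for patients under 45 kg

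*Combined protocol and SAP*

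**What the plan says.** Sections 3.1.2 and 5.3 set dosing by weight and body surface because the study takes both children and adults. Section 4.1 opens entry at age 1.

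Section 3.3.1 lets the investigator lower the dose for safety: "the dose may be temporarily or permanently reduced to 9" µg/day, with 5 µg/m²/day given for patients under 45 kg. The next sentence names both low doses again and allows escalation after at least 7 days, with the full dose also given for both weight groups. It then offers the alternative: "or treatment may be continued at the dose of 9" µg/day. No under-45 kg figure follows. Section 3.3.1 runs on for several paragraphs after this clause, so the clause ends its own paragraph and not the section.

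Section 7.5 lists removal criteria for CNS events that are probably or definitely related to blinatumomab. Its fourth bullet reads "A CTCAE Grade 3 CNS-related adverse event leading to treatment interruption that occurred at a dose of" 9 µg/day, again with no figure for patients under 45 kg. The treatment rule that it mirrors, in section 3.3.2, begins "A grade 3 CNS event leading to treatment interruption at the dose of 9" µg/day and does give 5 µg/m²/day. Table 2 has a separate column for patients under 45 kg, where the rule for grade 3 neurological toxicity begins "If the toxicity occurred at 5" µg/m²/day and ends in permanent discontinuation.

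**The concern.** Both places are operative text. One is a dosing instruction for a patient whose dose has already been lowered for safety. The other decides who leaves the study. Each prints the figure for the heavier weight group as if it applied to everyone, in a protocol that elsewhere takes care to give two figures.

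At stake are two things: whether the number printed in 3.3.1 is right for a patient under 45 kg, and whether 7.5 reaches the same patients as the permanent-stop rule in 3.3.2 and Table 2.

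**Working it through.** **Step 1. Count the statements of the low dose.** Each Table 2 instruction is counted once across its two weight columns.

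| Place | Statement | Under-45 kg figure given? |
|---|---|---|
| 3.3.1 | Restart after grade 3 cytokine release or coagulopathy | Yes |
| 3.3.1 | Discretionary reduction | Yes |
| 3.3.1 | Minimum 7 days at the low dose | Yes |
| 3.3.1 | Alternative of staying at the low dose (same sentence as the row above) | **No** |
| 3.3.1 | Start of cycle 1.1 ("For cycle 1.1, subjects will be started at 9" µg/day) | Yes |
| 3.3.2 | New cycle after a CNS event | Yes |
| 3.3.2 | Toxicity at the low dose | Yes |
| 3.3.2 | Grade 3 CNS event at the low dose | Yes |
| Table 2 | Cytokine release, grade 3: restart | Yes |
| Table 2 | Neurological, grade 3: restart | Yes |
| Table 2 | Neurological, grade 3: stop if at the low dose | Yes |
| Table 2 | Other reactions, grade 3: restart | Yes |
| 7.5 | Fourth bullet | **No** |

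With the figure: 4 in 3.3.1 + 3 in 3.3.2 + 4 in Table 2 = 11. Without it: 2. Total: 13.

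**Step 2. Is 9 µg/day the wrong number under 45 kg?** The two low doses coincide where 5 × BSA = 9, that is, at BSA = 9/5 = 1.80 m². At any smaller body surface 9 µg/day is the higher dose. The documents give no body sizes. On an assumed formula, BSA = √(cm × kg/3600), a patient at the 45 kg limit would need a height of 1.80² × 3600/45 = 259 cm to reach 1.80 m², and a lighter patient would need to be taller still. So the figure does not fit the group. This shows only that the number is wrong. It does not measure any dose that would be given.

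**Step 3. Can the intended dose be recovered in 3.3.1?** Yes. The sentence starts from a patient who has spent at least 7 days on 9 µg/day or, under 45 kg, on 5 µg/m²/day. A patient can only *continue* on the dose already being given, which under 45 kg is 5 µg/m²/day.

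**Step 4. Whom does 7.5 leave out?** Take a patient under 45 kg with one grade 3 CNS event at 5 µg/m²/day, probably or definitely related, that leads to interruption.

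- First bullet (more than one seizure): does not apply.
- Second bullet (grade 4): does not apply.
- Third bullet: "A CNS-related adverse event leading to treatment interruption that requires more than one week to resolve to CTCAE Grade" 1 or less. This removes the patient at any dose if resolution takes more than a week.
- Fourth bullet: read literally, it applies only at 9 µg/day.
- 7.3 needs a grade 4 event. 7.4 needs a related interruption of more than 2 weeks, and would apply only if a permanent stop is read as an interruption.

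What remains is the event that resolves to grade 1 or less within a week. For that patient 3.3.2 and Table 2 both require permanent discontinuation, so the drug stops and only removal from study is left open.

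**Step 5. Does either omission reach the statistics?** No. Section 8.3.5 monitors all treated patients, and its toxicity definition is built on grade 3–4 acute GVHD, secondary graft failure and early non-relapse mortality. It does not list CNS events or the dose received. Nothing in Tables 5 and 6 depends on either clause.

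**The case against.** The strongest reply is that this is close to copy-editing. In 3.3.1 the correct dose stands earlier in the same sentence, and the step is taken only after consultation with the investigator. In 7.5 the safety action is already secured, since 3.3.2 and Table 2 stop the drug for both weight groups. Section 7 does not mirror section 3.3 exactly in any case: 3.3.1 stops the drug for grade 4 events that are at least possibly related, while 7.3 removes patients only for probably or definitely related ones. A patient can therefore already be permanently off drug without meeting a removal criterion.

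All of that stands, and it sets the level of the point. It does not make the two clauses correct. A dosing instruction should print the right figure for each group it covers, and a removal criterion should cover the same weight groups as the rule it repeats.

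Two stronger readings are tempting. A reader might infer that children whose dose was lowered for safety would be overdosed by the ratio of 9 µg/day to their body-surface dose. The documents do not support this, because the sentence directs continuation of the current dose and the paired dose is printed in it. A reader might also infer that 7.5 lets such a patient go on receiving blinatumomab. It does not, because the permanent stop applies regardless of 7.5.

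**Conclusion.** The point holds as a minor internal inconsistency: both clauses are wrong as written for patients under 45 kg, and they are 2 of 13 statements of the low dose. In 3.3.1 the intended dose is clear and a dosing error is unlikely. In 7.5 the literal gap is confined to patients under 45 kg with a probably or definitely related grade 3 CNS event at 5 µg/m²/day that resolves to grade 1 or less within a week, and it concerns study removal alone. No overdose and no effect on the feasibility conclusion is claimed.

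The count rests on the convention stated for Table 2. That the number is wrong rests on the protocol's own paired doses; the height figure adds an assumed body-surface formula, and the conclusion does not need it.

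**What to change.** After 9 µg/day, insert (or 5 µg/m²/day if < 45 kg) in two places: the clause that ends the discretionary dose-reduction paragraph of 3.3.1, and the fourth bullet of 7.5. This matches the wording used for cycle 1.1 in 3.3.1 and in 3.3.2, agrees with Table 2, and makes all 13 statements consistent. The sponsor's clinicians should confirm the figure.

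The cost is two short insertions, which can go into the next amendment or a clarification letter. Design, sample size, stopping boundaries and analysis stay as they are.
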